2.2. Data and Safety Monitoring Board

An independent Data and Safety Monitoring Board (DSMB) will review accumulating pharmacodynamics, pharmacokinetic, and safety data to ensure the continuing safety of the study subjects and the integrity of the study. The DSMB will meet once before the study begins and at 2 scheduled points during the study. There will be both an open and closed session at each DSMB meeting where study data are reviewed. During open sessions, representatives of the study sponsor and study implementor may be present, and information will be provided and discussed in a blinded fashion. During closed sessions only the DSMB members, the DSMB Executive Secretary (to take notes only), and an FHI 360 statistician (to answer questions about

the analysis) will be present to discuss results by treatment group. Details of the DSMB procedures and responsibilities are documented in a separate DSMB Operational Plan.

2.3. Sample Size and Power Considerations

Part 1 is not powered to definitively assess pharmacokinetics. Rather, if the pharmacokinetics profile of undiluted TV-46046 appears consistent with a safe and efficacious 6-month injectable contraceptive method, then 3 dose levels within the dose range of 80 to 300 mg will be recommended for Part 2. Likewise, the study size for Part 2 was not chosen to make definitive conclusions regarding the effectiveness of TV-46046 in the range of doses selected. However, up to 20 subjects per group should be sufficient to provide meaningful insights into the distributions of pharmacokinetics and pharmacodynamics outcomes, and to inform selection of a dose for further study. Scientific judgment will be used to determine if the sample size in Part 2 can be reduced from 20 subjects per group, depending on the variability of parameter estimates observed in Part 1. Participants who are withdrawn from the study will not be replaced.

2.4. Sequence of Planned Analyses

2.4.1. Planned Interim Analyses

There are five planned reviews of the interim Part 1 and Part 2 data as outlined below, but the number and timing of reviews may change based on interim findings.

- The 1st planned interim analysis will be performed after the 6 subjects in Cohort 1A
 of Part 1 (receiving undiluted TV-46046) have completed 1 month of post-injection
 follow-up, and is intended to inform the early part of the pharmacokinetic profile.
- The 2nd interim analysis will be performed after the same 6 subjects in Cohort 1A of Part 1 have completed 4 months of post-injection follow-up, and is intended to inform the decision to move into, and the selection of doses for Part 2.
- The 3rd and 4th interim analyses are planned to occur after 50% of subjects in Part 2
 have completed 4 and 7.5 months of post-injection follow-up, respectively, and are
 intended to help inform the decision to move to, and the dose selection for further
 clinical study.
- The 5th and final planned interim analysis is planned to occur when 100% of subjects in Part 2 have completed 7.5 months of post-injection follow-up (the entire intended dosing interval, plus 1.5 months). A preliminary report of study findings based on this analysis may be submitted to the U.S. Food and Drug Administration (FDA) as part of the planning phase for future studies.

Among these 5 planned interim analyses, the DSMB may only convene to review data prior to initiation of Part 2 (2nd planned interim analysis) and at the first interim analysis of Part 2 data (3rd planned interim analysis), with the other analyses used by the clinical team to inform the design of Part 2 and/or the product development program. However, the DSMB may request review of other planned or unplanned interim analyses for purposes of monitoring participant safety or to make recommendations regarding modifications to the study.

2.4.2. Final Analyses and Reporting

All final analyses identified in this SAP will be performed after the last participant has completed the study, although an earlier report of data collected through month 7.5 of follow-up

Statistical Analysis Plan Version 2.0

in Part 2 may be submitted to the FDA in advance of any planning meetings for future studies. Any supportive analyses which were not identified in the SAP prior to unblinding of statisticians will be documented as exploratory in the CSR.

3. ANALYSIS SETS

In the definitions that follow, an Analysis Population refers to a particular set of study subjects and an Analysis Set refers to the time contributed to analyses by subjects in a given population. Unless otherwise noted, the definitions for inclusion in these analysis populations and sets are assumed to be the same for Part 1 and Part 2.

3.1. Screened Population

The Screened Population consists of all screened participants who are consented to participate in the study, regardless of their enrollment status.

3.2. Treated Population

The Treated Population consists of all screened participants who are enrolled and receive a dose of study drug, and is the primary population for safety and acceptability analyses. The corresponding *Treated Analysis Set* includes all baseline and follow-up data contributed by participants in the Treated Population. Analyses will be performed based on treatment received. In the event of randomization errors, failure to follow the intention-to-treat principle will be justified on the grounds that the study will not be used to make definitive conclusions regarding the efficacy of TV-46046.

3.3. Primary Evaluable Population

The Primary Evaluable Population is a subset of the Treated Population, excluding subjects who have detectable MPA in their baseline specimen (more than 5% of their individual C_{max}) or for whom a major protocol violation occurred at enrollment, including: the absence of a confirmed ovulation in the pre-treatment period; BMI outside the eligible range (with the exception of the 6 subjects purposefully enrolled with BMI ≥40 in Part 2); or use of drugs known to impact ovulation or the pharmacokinetics of MPA (with the exception of selective COX-2 inhibitors that are taken for fewer than 5 consecutive days). The *Primary Evaluable Analysis Set* includes all time contributed by participants in the Primary Evaluable Population during which a pharmacokinetic or pharmacodynamics outcome is assessed, up to the initiation of any medication known to impact ovulatory function or the pharmacokinetics of MPA.

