# 5.3. Prior and Concomitant Medication or Treatment

Any prior or concomitant therapy, medication, or procedure a subject has had within 30 days before study drug administration and up to the final visit will be recorded on the CRF. During the scheduled follow-up visits, the investigator will ask subjects whether they have taken any medications (other than study drug), including over the counter (OTC) medications, vitamins, or herbal or nutritional supplements, since the previous visit. During laboratory visits information of the use of concomitant medications will be documented only if reported by the subject. Generic or trade name, indication, route of study drug administration, dosage, and start and end dates will be recorded.

Any drugs that may interfere with metabolism of MPA or affect ovarian function will be prohibited during the study. The following medications should not be used during this study (unless medically indicated):

- rifampicin
- griseofulvin
- anticonvulsants
- barbiturates
- antiretroviral drugs (ARVs): non-nucleoside reverse transcriptase inhibitors (efavirenz, nevirapine) and ritonavir-boosted protease inhibitors
- aminoglutethimide
- St. John's wort
- selective cyclooxygenase-2 (COX-2) inhibitors (eg, meloxicam, celecoxib) for 5 or more consecutive days
- steroids (synthetic estrogens, progestins, androgens)

<sup>4 Band-Aid is a registered trademark of Johnson & Johnson Corporation.

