#### 8.2.3. Primary Evaluable Population

The Primary Evaluable Population is a subset of the Treated Population, excluding subjects who have detectable MPA in their baseline specimen (more than 5% of their individual  $C_{max}$ ) or for whom a major protocol violation occurred at enrollment, including: the absence of a confirmed ovulation in the pre-treatment period; BMI outside the eligible range (including the 6 subjects purposefully enrolled with BMI  $\geq$ 40); or use of drugs known to impact ovulation or the pharmacokinetics of MPA. The Primary Evaluable Analysis Set includes all time contributed by participants in the Primary Evaluable Population during which a pharmacokinetic or pharmacodynamic outcome is assessed, up to the initiation of any concomitant medication known to impact ovulatory function or the pharmacokinetics of MPA.

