## 8.5.3. Planned Method of Analysis

There are 5 planned reviews of the interim data; 2 reviews in Part 1 and 3 reviews in Part 2, although their number and timing may change based on the findings. The 2nd interim data review in Part 1 is intended to inform the decision to move into, and the selection of doses for, Part 2. The timing of interim data reviews may change based on the findings. For details, see Section 8.10.

For both Part 1 and Part 2, individual MPA profiles will be displayed through month 12 following treatment initiation or earlier date of withdrawal from the study using the Primary Evaluable Analysis Set, with any post-baseline MPA concentrations that fall below the limit of quantification (LOQ) replaced by half the applicable LOQ. If 120 mg/mL is selected as one of the doses in Part 2, then subjects in that treatment group in Part 1 will be incorporated in the Part 2 pharmacokinetics analysis. Data from the subset of 6 subjects (2 per treatment group) with extreme obesity (BMI  $\geq$ 40) in Part 2, and subjects with detectable MPA at baseline or who used drugs known to interfere with pharmacokinetics or pharmacodynamics of MPA prior to return to ovulation, will be excluded from the primary analysis but will be described separately. Sparse data collected after month 12 will likewise be described separately for the subset of subjects who

have not ovulated by month 12. Pharmacokinetic parameters will be estimated for each subject in the Primary Evaluable Population using non-compartmental analysis.

Summaries of pharmacokinetics parameters and metrics will include means, medians, geometric means, minima, maxima, as well as standard deviation (SD), percent coefficient of variation (%CV) and 95% CIs for means and geometric means. The time to achieve MPA concentration greater than 0.2 ng/mL, and the number and percentage of subjects with MPA serum concentrations below 0.1 ng/mL and 0.2 ng/mL at days 182 and 210, will likewise be summarized by treatment group. Treatment group comparisons will be based on 90% confidence intervals for geometric mean ratios of pharmacokinetic parameters or analysis of covariance based on log-transformed responses. Specific variables included in covariate adjusted analyses (eg, age, BMI) will be specified in the separate statistical analysis plan.

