10. PHARMACOKINETICS ANALYSIS

For both Part 1 and Part 2, individual MPA profiles will be displayed (both in the original scale and using semi-log plots) through month 12 following treatment initiation or earlier date of withdrawal from the study using the Primary Evaluable Analysis Set, with post-baseline MPA concentrations that fall below the limit of quantification (LOQ) replaced by half the applicable LOQ. If 120 mg/mL is selected as one of the Part 2 dose groups, then subjects in that Part 1 group will be incorporated in the primary Part 2 pharmacokinetics analysis. Data from the subset of 6 subjects (2 per dose group) with extreme obesity (BMI ≥40) in Part 2, and subjects with detectable MPA at baseline or who used drugs known to interfere with pharmacokinetics or pharmacodynamics of MPA prior to return to ovulation, will be excluded from the primary analysis but will be described separately. Sparse data collected after month 12 will likewise be described separately for the subset of subjects who have not ovulated by month 12.

The following non-exhaustive list of pharmacokinetic parameters and metrics will be estimated based on non-compartmental analysis implemented using Phoenix WinNonlin® or a validated SAS® macro (Matos-Pita 2005): C_{max}, t_{max}, C₉₁, C₁₈₂, C₂₁₀, AUC₀₋₉₁, AUC₉₁₋₁₈₂, AUC₀₋₁₈₂, AUC₀

Summaries of pharmacokinetic parameter estimates in each treatment group will include means, medians, GMs, minima, maxima, SD, %CV, and 95% CIs for GMs. The number and percentage of participants with C₁, C₉₁, C₁₈₂ and C₂₁₀ below 0.1 ng/mL and 0.2 ng/mL, and the time above 0.1 ng/mL, will be summarized by group. The predicted drug accumulation after repeat dosing will be based on observed mean drug concentrations at months 6 and 12 (when routine PK testing ends). Steady state concontrations will be predicted using an appropriate PK model for drug concentrations at months 18, 24, etc., following each successive hypothetical dose given at 6-month intervals.

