13. CHANGES TO ANALYSES SPECIFIED IN PROTOCOL V1.0

13.1. Changes from V1.0 of protocol, Prior to Study Initiation

The protocol was amended twice prior to study initiation (original protocol: 01 May 2016; amendment 1: 29 May 2016; amendment 2: 04 November 2016). This section described changes to planned statistical analyses based on amendments 1 and 2, which were incorporated in V1.0 of the SAP.

- Addressed amendment 01 of protocol regarding timing of menstrual bleeding and related acceptability data.
- Specified that only participants with baseline MPA exceeding 5% of their individual C_{max} will be excluded from the Primary Evaluble Population. This change was made corresponding to the change in Protocol Amendment 2, Section 8.2.3 (Primary Evaluable Population).
- Specified selective Cox-2 inhibitors (eg, Meloxicam or Celecoxib) that are taken for fewer than 5 consecutive days will not lead to exclusion from the Primary Evaluable Population or Analysis Set. This change was made in responding to the change in Protocol Amendment 2, Section 5.3 (Prior and Concomitant Medication or Treatment)

13.2. Changes from V1.0 of SAP, After Initiation of Part 1 (26 October 2016) but Prior to Availability of any PK/PD data, including changes made in anticipation of Protocol Amendment 3 (27 March 2017)

- Changed method for estimating MPA accumulation following 2 or more hypothetical
 doses delivered at 6-month intervals. The method specified in V1.0 of SAP assumed a
 one-compartmental EV-model obeying monophasic decay which may or may not
 apply for TV-46046. Revised method is based on observed mean drug concentrations
 at month 6 and month 12 (when regular PK sampling ends), and an appropriate model
 for predicting drug concentrations at subsequent 6-month intervals.
- Changed plans for descriptive analyses of E2 data. This change was made to clarify the analyses of E2 described in SAP V1.0.
- Protocol Amendement 3 included language to the effect that fewer than 3 doses could be selected for Part 2, as well as new safety measures for Part 2, including: mood and liver function testing at the week 13, week 32, and finals study visit; weekly electronic diary data; menstrual bleeding pattern.

13.3. Changes from V1.0 of SAP, After initial Interim Review of PK/PD data (27 March 2017)

- Clarified visit window for monthly mensutrual bleeding data

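### SAP 3.3 lets a drug that acts only on ovulation end a woman's MPA series, omits the short-course COX-2 exception that SAP 13.1 says applies, and disagrees with SAP 10 and Protocol 8.5.3

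*SAP*

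**What the plan says.** Protocol 5.3 gives two separate reasons for prohibiting a drug: "Any drugs that may interfere with metabolism of MPA or affect ovarian function will be prohibited during the study". Its list then names selective COX-2 inhibitors only for courses of 5 or more consecutive days, and gives no reason for any individual item.

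SAP 3.3 merges the two reasons. The Primary Evaluable Analysis Set holds a woman's PK and PD time "up to the initiation of any medication known to impact ovulatory function or the pharmacokinetics of MPA". Protocol 8.2.3 has the same combined rule ("up to the initiation of any concomitant medication known to impact ovulatory function or the pharmacokinetics of MPA"). Neither lets her back in once a course has ended.

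The COX-2 exception in SAP 3.3 reads "with the exception of selective COX-2 inhibitors that are taken for fewer than 5 consecutive days". It sits in the Population sentence, on drug use at enrolment, and is not repeated in the Analysis Set sentence. SAP 13.1 describes it more broadly: selective COX-2 inhibitors "taken for fewer than 5 consecutive days will not lead to exclusion from the Primary Evaluable Population or Analysis Set".

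Two further statements bear on which MPA data are analysed. SAP 10 displays the MPA profiles through month 12 or earlier "withdrawal from the study using the Primary Evaluable Analysis Set". It then says that women who used drugs interfering with the PK or PD of MPA before return to ovulation leave the primary analysis and are described separately. Protocol 8.5.3 says: "Pharmacokinetic parameters will be estimated for each subject in the Primary Evaluable Population using non-compartmental analysis".

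**The concern.** The Part 1 primary endpoints are MPA profiles and parameters derived from them. Protocol 3.3 samples MPA to week 52 whether or not the woman has ovulated, so the design itself treats the PK series as independent of ovulation. A drug that alters ovulation but not MPA levels gives no PK reason to stop using her concentrations.

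The samples at risk are the late ones. C182, AUC0-182, terminal half-life and AUC0-∞ answer the Part 1 question of whether levels last 6 months. Part 2 was never implemented (SAP 13.3), so cohorts of 6 are all the PK data this study will give. In addition, an analyst who follows the SAP 3.3 sentence literally would go against the decision that SAP 13.1 records on short COX-2 courses.

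**Working it through.** The plan states no power or precision figure for Part 1, so there is none to reproduce. The check compares the texts and then sizes the effect.

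**1. Does the cut-off reach MPA data?** Yes for the profiles, since SAP 10 names the Analysis Set for them. SAP 4.3 also gives date-imputation rules for censoring due to excluded medication, so the cut-off is meant to operate. For the non-compartmental parameters it is unclear: Protocol 8.5.3 names the Population, which carries no time cut-off, and in the text that can be read SAP 10 ties the set to the profile displays.

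**2. Do SAP 3.3 and SAP 10 give the same result?** They do not:

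| Drug acts on | Start, relative to return to ovulation | SAP 3.3 | SAP 10 drug rule |
|---|---|---|---|
| ovulation only | before | MPA series cut at start | woman out of the primary analysis |
| ovulation only | after | MPA series cut at start | no effect |
| MPA levels | before | MPA series cut at start | woman out of the primary analysis |
| MPA levels | after | MPA series cut at start | no effect |

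Under SAP 10, whether a woman counts for PK depends on a PD event. A drug that does change MPA levels has no consequence there if she has already ovulated.

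**3. Samples lost under a literal reading of SAP 3.3.** Scheduled MPA samples (Protocol 3.3) are 14 from day 0 to day 42, 14 from week 8 to week 32, and 5 at weeks 36, 40, 44, 48 and 52: 14 + 14 + 5 = 33.

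- Start just after week 13 (day 91): weeks 15 to 32 give 10, plus 5, so 15 of 33 are lost.
- Start just after week 26 (day 182): weeks 28, 30 and 32, plus 5, so 8 of 33 are lost.
- Start just after week 32: 5 of 33 are lost.

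**4. What happens to the parameters.** SAP 14 fits λ to the last three or more usable samples from t_max onward. If t_max is day 42 or earlier, a woman cut just after week 13 still has day 42 and weeks 8, 10, 12 and 13, which is at least five points. λ is then reportable if the slope is negative, and AUC0-∞ follows as AUC0-last + C_last/λ. SAP 14 imputes a partial-AUC end concentration from λ after discontinuation or a first LOQ value. It does not name a medication cut-off, although SAP 4.3 refers missing values at key time points to SAP 14 in general terms. The likelier result is therefore extrapolation from earlier samples rather than a missing woman. The extrapolation may use a slope fitted before the true terminal phase.

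**5. If a parameter is lost (illustration).** The 95% CI half-width for a log geometric mean, in SD units, is t(0.975, n−1)/√n.

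- n = 6: 2.571/2.449 = 1.049
- n = 5: 2.776/2.236 = 1.242, ratio 1.18
- n = 4: 1.591, ratio 1.52

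For the 90% CI of a geometric mean ratio, t(0.95, n1+n2−2)·√(1/n1+1/n2) is 1.046 for 6 v 6 and 1.110 for 5 v 6, a ratio of 1.06.

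**6. How often it might occur.** The documents give no use rate. If 5%, 10% or 20% of women took such a drug (assumed), the chance of at least one in a cohort of 6 is 1 − (1 − p)^6 = 26.5%, 46.9% or 73.8%.

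**The case against.** The other side has four good points.

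- **The loss is not shown to occur.** Planned use of prohibited drugs is an exclusion criterion (Protocol 4.2, item v), no use rate is given, Part 1 is expressly not powered, and data removed by the SAP 10 rule are still described separately. This stands. A reader might infer that valid primary PK data are being discarded; the documents support only a conditional risk.
- **Short COX-2 courses are protected by SAP 13.1, and Protocol 5.3 does not prohibit them.** A reader might infer that the SAP instructs analysts to drop those data. It does not: the decision is clear and the sentence in SAP 3.3 has not been brought into line with it.
- **COX-2 inhibitors are not shown to be free of effect on MPA levels.** A reader might take the cited study of meloxicam and ovulation as the reason for the prohibition. Protocol 6.2 cites it only among sources for progesterone criteria, so classing COX-2 inhibitors as acting on ovulation alone is not supported.
- **One conservative set was prespecified in both documents, and relating MPA concentration to ovulation is a stated objective.** That justifies a combined cut-off for the concentration–ovulation analysis. It does not justify one for the Part 1 MPA endpoints, and it does not explain why SAP 3.3 and SAP 10 give different results.

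A reader might also infer that an early drug start removes a woman from every late parameter. Step 4 shows that this need not follow.

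**Conclusion.** The point holds as a defect of definition. SAP 3.3 ends MPA follow-up for a reason that need not concern MPA, and its Analysis Set sentence omits an exception that SAP 13.1 says it has. SAP 10 applies a second rule that conflicts with the first, and Protocol 8.5.3 leaves it open whether the cut-off reaches the non-compartmental parameters.

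The size is conditional. For starts between week 13 and week 32, between 15 and 5 of 33 scheduled MPA samples go. For the earlier starts in that range, day-182 and AUC0-182 results would rest on extrapolation; for any of them the late samples for the terminal slope are missing. The 18% widening applies only if a parameter is actually lost for one of 6 women at unchanged SD. It is an illustration, not an expected loss. The conclusion assumes that at least one drug on the Protocol 5.3 list affects ovulation without altering MPA levels. The two-part wording of that section implies this, but the documents do not establish it drug by drug.

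**What to change.** 1. In the Analysis Set sentence of SAP 3.3, repeat the exception for selective COX-2 inhibitors taken for fewer than 5 consecutive days, so that it matches SAP 13.1.
2. Define two cut-offs. For MPA and PK analyses, stop only at the start of a drug that alters MPA pharmacokinetics or itself contains MPA, whatever the ovulation status. For ovulation analyses, including the concentration–ovulation relationship, stop at the start of a drug of either kind.
3. Have the sponsor's pharmacologist classify the Protocol 5.3 list into the two kinds, without presuming that COX-2 inhibitors act on ovulation alone. Part 1 is open-label and interim MPA data have been reviewed, so the classification should be made from the list, before the final analysis and without reference to which women took what.
4. Replace the drug rule in SAP 10 with the PK cut-off, state which set the non-compartmental analysis uses, and say in SAP 14 how end-times beyond a medication cut-off are handled. Keep the combined rule as a sensitivity analysis.

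The cost is SAP wording and a one-off classification of an existing list; no new data are needed. Under the SAP's own introduction, the resulting difference from Protocol 8.2.3 and 8.5.3 is to be explained in the clinical study report.
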